#### 4.3 Scientific Rationale

Long-term survival after solid organ transplantation has increased during the last decades (23) due to improvements in surgical technique, peri-operative care, and more efficient IS. However, transplant recipients still exhibit higher morbidity and mortality than the general population. One of the main causes are co-morbidities negatively influenced by chronic IS drug usage (24). Minimization (or complete withdrawal) of IS, particular CNIs, may overcome these problems and has become a priority goal in transplantation. The clinical opportunity is more tangible in the liver than in other transplantation settings due to the greater capacity of the liver allograft to cope with the cytolytic effects of alloimmune responses. The potential benefits of IS minimization or withdrawal, however, still need to be balanced with the risks and inconveniences of prompting liver allograft rejection. The recent observation that operational tolerance can be predicted employing a combination of clinical parameters and molecular biomarkers would modify the equipoise in favour of discontinuing IS in previously identified operationally tolerant recipients. Identification of a reproducible and reliable tolerance signature would therefore substantially benefit the liver transplant population. In Europe approximately 6000 liver transplants are performed every year (700 of them in the UK). Under the current standard-of-care indefinite pharmacological IS is prescribed to all of them. The cost of immunosuppressive drugs is £3000- £5000/patient/year. In addition to its cost, chronic IS results in substantial side effects (hypertension, diabetes, renal failure, hyperlipidaemia, cancer, infections) that contribute to patient morbidity and mortality. The implementation of tolerance biomarkers would reduce the cost of medical management in liver transplantation, reduce the negative impact of co-morbidities associated with the use of chronic IS, and increase the quality of life of liver recipients.

The recent prospective, multi-centre drug withdrawal trials conducted in Europe and in the US and described above have been major breakthroughs in the field (12, 13). First, they have identified the subgroups of liver recipients more likely to benefit from IS withdrawal. Second, they have demonstrated that in hepatitis C negative liver recipients operational tolerance can be predicted by measuring the expression of a 5-gene signature in liver biopsies, while blood transcriptional biomarkers lack sufficient reproducibility. Third, they have identified novel mechanisms likely to be

involved in the spontaneous development of immune tolerance (e.g. role of iron metabolism, immunosenescence, influence of anti-HLA antibodies), some of which could have implications beyond liver transplantation. These recent studies provide the rationale and clinical opportunity to perform, for the first time, a randomised controlled trial of IS withdrawal to test the clinical utility and safety of a biomarker test of liver transplant tolerance.

# 5. TRIAL OBJECTIVES AND DESIGN

# 5.1 Objectives

The overall objective is to assess the clinical utility and risk/benefit ratio of employing a previously validated transcriptional test of tolerance to stratify liver recipients prior to IS withdrawal.

### 5.2 Primary Objective:

To determine if the use of a liver tissue transcriptional test of tolerance to stratify liver recipients prior to IS withdrawal accurately identifies operationally tolerant recipients and reduces the incidence of rejection, as compared with a control group in whom IS withdrawal is performed without stratification.

### 5.3 Secondary Objectives:

- 1) To establish the safety of biomarker-guided IS withdrawal.
- 2) To determine the health-economic impact of withdrawing IS in liver transplant recipients and to assess how much this cost is influenced by the use of a diagnostic test of operational tolerance.
- 3) To assess the effect of IS withdrawal on the quality of life of liver transplant recipients.
- 4) To determine the extent to which IS withdrawal improve drug-related co-morbidities.
- 5) To investigate if liver transplant recipients under IS become operationally tolerant over time.
- 6) To determine if the presence of donor-specific anti-HLA antibodies influence the success of IS withdrawal, and whether IS withdrawal promotes the development of anti-HLA antibodies in liver transplant recipients.
- 7) To explore the association between operational liver transplant tolerance, iron metabolism, immunosenescence, and specific gut microbiome profiles.

### 5.4 Trial Design

This is a prospective, multi-centre, phase IV, biomarker-strategy design trial with a randomised control group in which adult liver transplant recipients will undergo IS withdrawal. Enrolled participants will be randomised 1:1 to either: 1) Non-Biomarker-based IS weaning (Weaning-All; Arm A); or 2) Biomarker-based IS weaning (Arm B). In participants allocated to Arm A IS will be withdrawn regardless of the result of the biomarker test. Among participants allocated to Arm B, only those found to be biomarker-positive (Arm B+, i.e. potentially tolerant) will be offered IS withdrawal, while biomarker-negative participants (Arm B-, i.e. potentially non-tolerant) will remain on their

baseline maintenance IS. This will allow us to demonstrate that the biomarker is a useful test to personalise IS by offering drug withdrawal only to those participants who are likely to complete the process successfully, avoiding unnecessary rejections among those who have not developed tolerance. Comparing the outcome of IS withdrawal between arms A and B+ will provide direct evidence of the clinical usefulness of the test as a function of its predictive accuracy. We have established that for the biomarker to drive safe IS withdrawal its Positive Predictive Value  $(PPV = \frac{Number Actually Tolerant}{Number Biomarker+})$  should be no less than 0.80, and its sensitivity at least 070. To account for centre effects, we will use stratified randomization. Furthermore, to avoid biases, participants undergoing drug withdrawal and their physicians will be blinded to the biomarker results. Participants randomized to Arm B- will know their biomarker status, and will be maintained in the study until they complete 48 months of follow-up post randomisation. They will contribute to secondary clinical outcomes and to the evaluation of the stability of the tolerance signature.

Cost and quality of life (HrQOL) assessments will be conducted alongside the trial to estimate the health-economic implications of the 2 different strategies. Furthermore, sequential biological specimens will be collected to conduct ancillary mechanistic studies. Recruitment will take place in 14 European liver transplant units (King's College Hospital, Royal Free London, Newcastle, Birmingham, Leeds, Edinburgh, Cambridge, Leuven, Hannover, Berlin, Barcelona, Dublin, Cliniques Universitaires Saint-Luc and Palermo-ISMETT).

### 5.5 Trial Duration

Estimated recruitment period: 18 months.

Individual patient follow-up following enrolment: 48 months (6-12 months drug weaning, 36 months post-weaning follow-up).

Total estimated study duration: 72 months.

## 6. STUDY POPULATION

#### 6.1 Inclusion Criteria

Participants *must meet all* of the following criteria to be eligible for this study:

- At the time of screening: more than 3 years post-transplant if participants are ≥50 years old, OR ≥ 6 years post-transplant if participant age is ≤50 years old.
- 2. Recipient of either deceased or living donor liver transplant.
- 3. Recipient of single organ transplant only
- 4. Liver function tests: direct bilirubin  $\leq$ 17.1 umol/L and ALT  $\leq$ 60 IU/L at the screening visit.
- 5. On calcineurin inhibitor (CNI) IS with or without one of the following: Low dose mycophenolic acid (≤ 1080 mg daily), mycophenolate mofetil (MMF ≤ 1500 mg daily), azathioprine (≤ 150 mg daily), sirolimus/everolimus; or on monotherapy with sirolimus/everolimus or mycophenolate/mycophenolic acid monotherapy (effective contraception must be used

before beginning mycophenolate therapy, during therapy, and for six weeks following discontinuation of therapy, see Appendix 6),

6. Ability to sign informed consent.

# 6.2 Exclusion Criteria

Participants who meet any of the following criteria will not be eligible for this study:

- 1. Serum positivity for HCV-RNA
- 2. Serum positivity for HIV-1 infection, HBV surface antigen or HBV-DNA
- 3. Immune-mediated liver disease in which IS discontinuation is inadvisable (autoimmune hepatitis, primary sclerosing cholangitis, primary biliary cirrhosis).
- 4. Acute or chronic rejection within the 52 weeks prior to screening.
- 5. GFR <30 mL/min (to mitigate the risk of worsening renal failure should rejection occur and high level of CNI be required).
- 6. The need for chronic anti-coagulation that cannot be safely discontinued to safely perform for a liver biopsy.
- 7. Baseline (screening) liver biopsy showing any of the following: a) acute rejection according to Banff criteria; b) early or late chronic rejection according to Banff criteria; c) inflammatory activity and/or fibrosis in excess of permissive criteria (Table 1) (25); f) any other findings that might make participation in the trial unsafe. Eligibility will be determined by the central pathologist.
- 8. Patient age <18 years old at the time of transplant.
- 9. Pregnant females and females of childbearing age not using effective contraception (See Appendix 6).
- 10. Current illicit drug or alcohol abuse.
- 11. Inability to participate in frequent monitoring of liver function (every 3 weeks) and clinical visits during IS withdrawal.
- 12. Inability to comply with study directed treatment.
- 13. Any medical condition that in the opinion of the principal investigator would interfere with safe completion of the trial.
- 14. Participation in another clinical trial during the month prior to enrollment.

Compartment	Findings
Portal inflammation and interface activity	This is preferably absent, but minimal to focal mild portal mononuclear inflammation may be present. Interface necro-inflammatory activity is absent or equivocal/minimal and, if present, involves a minority of portal tracts and not generally associated with fibrosis.
Centrizonal/perivenular inflammation	Negative for perivenular inflammation.
Bile duct changes	Lymphocytic bile duct damage, ductopenia, and biliary epithelial senescence changes are absent unless there is an alternative, non- immunological explanation (e.g. biliary strictures).
Fibrosis**	Fibrosis (if present) should be mild overall, and portal-to-portal bridging should not be more than rare. Perivenular and peri-sinusoidal fibrosis should not be more than mild according to the Banff criteria.
Arteries	Findings for obliterative or foam cell arteriopathy are negative.
* Patients with underlying AIH	, HCV, PBC, or PSC are excluded.

Table 1. Baseline (Pre-weaning) Biopsy Findings Conducive to the Minimization of IS\* (25)

\*\* Fibrosis should be graded as follows (26): Portal/periportal: 0-3

Peri-sinusoidal: 0 – 3. Perivenular: 0-3.

#### 6.3 Patient withdrawal criteria

Participants may be prematurely terminated from the study for the following reasons:

- 1. the participant elects to withdraw consent from all future study activities, including follow-up;
- 2. the participant is "lost to follow-up";
- 3. the participant dies;
- 4. any participant who fails screening and is deemed ineligible to initiate IS withdrawal;
- 5. pregnancy.

Participants have the right to voluntarily discontinue study treatment or withdraw from the study at any time for any reason without any consequences

The investigator has the right to discontinue a participant from study treatment or withdraw a participant from the study at any time if it is in the best interest of the participant.

Any medical condition that the investigator or sponsor determines may jeopardize the participant's safety if she or he continues receiving the study treatment. Screening failures will not be randomized and will not count towards the final sample size.

#### 7. STUDY MEDICATION

At the time of enrolment participants will be treated with tacrolimus, cyclosporine, azathioprine, everolimus/sirolimus and/or mycophenolate mofetil/mycophenolic acid. All specified immunosuppressive pharmacological drugs are commercially available and are licensed and have marketing authorisations as part of the standard of care in liver transplantation. For the purpose of this trial these drugs are defined as IMPs (Investigational Medicinal Products). Each IMP is specified

by active substance only. The objective of the trial is not to gain further information about the background treatment, but to assess the safety and promise of the diagnostic biomarker test of tolerance as a tool to stratify liver transplant recipients prior to an attempt to immunosuppression discontinuation. For reference safety information for IMPs, Investigators should refer to the relevant current summary of product characteristics (SmPC). Patients on mycophenolate mofetil or mycophenolic acid will need to receive effective contraception that will be maintained until 6 weeks following the discontinuation of these drugs (please see Appendix 6 for details on acceptable forms of contraception).

#### 8. PLANNED INTERVENTIONS

#### 8.1 Screening and Biomarker Test

All participants will undergo a Screening Visit during which informed consent will be obtained, the medical records will be reviewed to assess potential eligibility, a screening liver biopsy will be conducted, and bloods will be drawn for mechanistic studies. The screening liver biopsy will be shipped to King's and employed to confirm histologic eligibility by the central pathologist. Subjects identified as eligible for the clinical trial based on all screening procedures will undergo the analysis of the liver tolerance transcriptional biomarker test. This will be conducted on a 3 mm fraction of the screening liver biopsy cylinder that will be preserved in RNAlater reagent and frozen prior to shipment. The study will collect data on the percentage of stable participants identified as clinically suitable but who do not qualify for IS withdrawal and the reason for disqualification. This will clarify the trial's relevance to the broader liver transplant population. Biological specimens obtained from patients considered non-eligible on the basis of the screening liver biopsy will be kept for future research provided specific consent has been obtained.

#### 8.2 Randomisation

Participants will be randomized 1:1 to either: 1) Non-Biomarker-based IS weaning (Arm A); or 2) Biomarker-based IS weaning (Arm B). In participants allocated to Arm A IS will be withdrawn regardless of the result of the biomarker test. Participants allocated to Arm B will be offered IS withdrawal only if they are classified as tolerant (Arm B+), while they will remain on maintenance IS if classified as non-tolerant (Arm B-).

#### 8.2.1 Randomisation Procedure

A patient identification number (PIN) will be generated by registering the patient on the MACRO eCRF system (InferMed Macro), after consent has been signed. This unique PIN will be recorded on all source data worksheets and used to identify the patient throughout the study. Authorised site staff will be allocated a username and password for the randomization system. Once a patient is consented, all baseline data collected and eligibility confirmed, the staff member will log into the randomization system (www.ctu.co.uk) and click 'randomisation – advanced' and select LIFT and

enter the participants details (including MACRO PIN). The 'help' section of the system has video demonstrations to aid new staff in using the system. Once randomized, the system automatically generates confirmation emails to key staff, with or without treatment allocation information, depending on their role in the study. Participants that withdraw will not be replaced; levels of attrition have formed part of the sample size calculation to accommodate this.

#### 8.2.2 Randomisation method

Randomisation will be via a 24 hour bespoke web based randomisation system hosted at the KCTU on a secure server. 148 adult liver transplant recipients will be randomised 1:1 at the level of the individual using the method of minimisation, stratified by site (11) and by the result of the Biomarker Test. The use of a random component in the minimisation algorithm will ensure that treatment allocation does not become deterministic and thus will protect pre-randomisation allocation concealment.

#### 8.3 Immunosuppression Withdrawal Protocol (Arms A and B+)

# Weaning from calcineurin inhibitor (CNI) or mycophenolate/mycophenolic acid monotherapy:

- Participants will initiate IS weaning after at least 3 weeks of stable liver function (as documented by 2 separated laboratory exams).
- Weaning will occur in eight 3-week intervals with each subsequent reduction based on liver function test stability over the prior 3-week interval.
- No single reduction should exceed 50% of the daily dose except the final reduction.
   Withdrawal will proceed as follows:
  - Reduce total daily dose to 75% current total dose x 3 weeks
  - Reduce total daily dose to 75% current total dose x 3 weeks
  - Reduce total daily dose to 50-75% current total dose x 3 weeks
  - Give above dose 5x weekly x 3 weeks with consolidation to once daily dose
  - Give current dose 4x weekly x 3 weeks
  - Give current dose 3x weekly x 3 weeks
  - Give current dose 2x weekly x 3 weeks
  - Give current dose 1x weekly x 3 weeks and discontinue

Effective contraception must be used before beginning mycophenolate/mycophenolic acid therapy, during therapy, and for six weeks following discontinuation of therapy (please see Appendix 6 for details on acceptable forms of contraception).

#### - Weaning from 2 IS drugs:

 Participants on 2 IS drugs will first undergo withdrawal of the CNI as described above. Once the participant has discontinued the CNI, at least 3 weeks of stable liver function documented by 2 sequential blood tests will be required before initiating withdrawal of the second drug. • Weaning of the mycophenolate/mycophenolic or azathioprine will occur in three 3-week intervals as follows:

-Reduce daily dose to approximately 66% of initial total dose x 3 weeks (e.g. in patients initially receiving MMF 1500mg daily dose, reduce to 1000mg daily dose).
-Reduce daily dose to approximately 33% of initial total dose x 3 weeks (e.g. in patients initially receiving MMF 1500mg daily dose, reduce to 500mg daily dose).
- Discontinue

### - Pausing of IS weaning:

 In the case of adverse events that could compromise safety, IS withdrawal can be temporarily paused for up to 4 weeks. During this time interval the participant will remain at the current dose. Participants are allowed up to 3 non-consecutive pauses. IS withdrawal will also be temporarily paused during the investigation of allograft dysfunction.

#### - Discontinuation of IS Weaning/Resumption of IS:

- Participants undergoing IS weaning who experience rejection will be re-started on IS and will not be allowed a second attempt.
- Participants who have successfully completed IS weaning and who subsequently experience rejection will be re-started on IS.
- Participants who cannot complete the IS weaning protocol and do not experience rejection will remain in the study but will be considered as 'failures'.

### 8.4 Maintenance Immunosuppression (Arm B-)

Participants randomized to Arm B and who are biomarker-negative will have no reduction in their IS for the first 12 months of study participation, except for the management of toxicity attributed to IS (as determined by the local investigator). For the remaining of the study, IS will be managed according to each centre's standard-of-care.

### 8.5 Management of Allograft Dysfunction

Allograft dysfunction is defined as any unexplainable elevation in ALT and GGT relative to baseline and above the upper limit of normality.

- When ALT and GGT are >100 IU/L a liver biopsy must be performed. Before indicating the liver biopsy, liver tests can be repeated for verification and re-assessment within 7 days. During this period of time IS withdrawal will be termporarily paused and participants will remain at their current IS doses.
- When ALT and/or GGT are <100 IU/L IS withdrawal will be temporarily paused and liver tests will be repeated within 7 days. In case of persistent allograft dysfunction with ALT and/or GGT <100 IU/L a liver biopsy can be performed or alternatively IS withdrawal can remain

paused for up to 4 weeks. Within 4 weeks IS must resume or a liver biopsy needs to be performed.

If a biopsy for cause has been performed and is non-diagnostic, then additional, follow-up biopsies will be performed at the discretion of the site investigator.

#### 8.6 Diagnosis and treatment of Rejection Episodes

Rejection episodes will be diagnosed on the basis of liver biopsy findings according to Banff criteria. Clinical decision will be made on the basis of local biopsy readings. Investigators can treat rejection episodes according to each centre's standard-of-care. The following are however the recommended guidelines:

- Allograft dysfunction with no acute rejection or indeterminate for acute rejection, and without other explanatory diagnosis should be treated, if the investigator chooses, with reinstitution of the baseline IS (regimen employed before initiation of IS withdrawal). If liver tests do not improve within 4 weeks, repeat biopsy should be considered prior to further escalation of treatment.
- Mild acute rejection should be treated initially with reinstitution of baseline IS. If liver tests do
  not improve within 2 weeks, dose increase or addition of 20 mg oral prednisolone (or equivalent)
  should be considered. Corticosteroids will be rapidly tapered down over a 4 week period. A
  second biopsy can be performed at any time at the investigator's discretion.
- Moderate acute rejection without jaundice and with mild biochemical abnormalities should be treated with reinstitution of baseline IS and 20 mg oral prednisolone (or equivalent) with rapid taper down of steroid doses over a 4 week period. If liver tests do not improve within 2 weeks, conversion or addition of another agent should be considered prior to corticosteroids. A second biopsy can be performed at any time at the investigator's discretion.
- Moderate acute rejection with marked biochemical abnormalities and/or jaundice, severe acute rejection, or chronic rejection, should be treated according to site standard of care. Antibody treatment should be reserved for steroid-resistant acute rejection proven by repeat liver biopsy.

#### 8.7 Reinstitution of IS following successful IS withdrawal

Patients who do not develop allograft dysfunction but in whom a protocol biopsy performed at 12 or 24 months after complete IS discontinuation reveales moderate inflammatory changes or other changes suggestive of progressive histological damage (as described in Table 5) will be treated with reinstitution of the baseline IS. Patients who do not exhibit any of the changes described in Table 5 but fail to meet the primary endpoint on the basis of the histological criteria defined in Table 4 will be maintained off IS until the end of the study.

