# 12. EFFICACY ASSESSMENT

#### 12.1 Definition of efficacy outcome measures

- Allograft dysfunction: any unexplainable elevation in ALT and GGT relative to baseline and above the upper limit of normality.
- Allograft rejection: will be defined on liver biopsy according to Banff criteria. In rare cases in which it may be not feasible or safe to await the performance of a liver biopsy, episodes of severe allograft dysfunction impairment occurring during weaning that cannot be attributed to any other etiology and that rapidly respond to the empirical re-initiation of immunosuppressive drug therapy will be considered as indicative of presumed allograft rejection.
- *Histopathology of acute allograft rejection:* Acute rejection will be defined by a liver biopsy exhibiting one of the following:

a) Presence of at least 2 of the following 3 features features according to Banff criteria:
 1) predominantly mononuclear portal tract inflammation containing lymphocytes, neutrophils and eosinophils; 2) inflammatory bile duct damage; 3) venous subendothelial inflammation of portal or central veins.

b) Portal and/or lobular inflammation without bile duct damage and subendothelial inflammation provided that: 1) the inflammatory lesions were not present in the baseline (pre-weaning) biopsy; 2) they cannot be attributed to any other etiology (drug toxicity, autoimmunity, viral hepatitis); and 3) they occur in the presence of allograft dysfunction that rapidly normalizes by the re-initiation of immunosuppressive drug therapy. This takes into consideration the fact that in long-term surviving liver transplant recipients acute rejection tends to exhibit less subendothelial inflammation and greater interface and lobular activity resembling chronic hepatitis).

- *Failure of IS withdrawal*: failure to complete IS withdrawal for any reason.
- Operational tolerance: successful withdrawal of IS and maintainance of normal allograft status, as assessed by the absence of allograft dysfunction 12 months after complete IS discontinuation, and by the lack of clinically-significant changes in the liver biopsy obtained 12 months after withdrawal as described in Table 4.

Compartment	Findings				
Portal inflammation and interface	Increased portal inflammation (in comparison with a pre-weaning biopsy				
activity	sample), especially in association with histopathological evidence of				
	tissue damage manifest as: focally worsening or more prevalent				

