	lymphocytic bile duct damage, interface hepatitis, fibrosis, or the				
	appearance of definite venous endotheliitis.				
Centrizonal/perivenular	New onset perivenular inflammation (in comparison with a pre-weaning				
inflammation	biopsy sample) associated with even mild perivenular necro-inflammatory				
	activity. Note: these changes might be present in the absence of typical				
	portal changes of rejection.				

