#### Table 5. Follow-Up Biopsy Findings in Patients Off IS that Should Prompt Re-Institution of IS

Compartment	Findings
Portal inflammation and interface activity	Development of moderate portal inflammation or moderate interface activity in most portal tracts.
Centrizonal/perivenular inflammation	Central perivenulitis in most central veins.
Bile duct changes	New-onset biliary epithelial cell senescence changes or ductopenia when sampling problems and/or an alternative, non-immunological explanation (e.g. biliary strictures) can be reasonably excluded
Fibrosis	At least a 2 grade increase in fibrosis in any one compartment (according to Venturi et al (26)).
Arteries	Any evidence of foam cell or obliterative arteriopathy

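### Section 8.3 restarts IS after any rejection and lacks an exception for silent protocol-biopsy rejection, which section 8.7 leaves untreated unless Table 5 is met

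*Protocol*

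**What the plan says.** Two sections say what happens after weaning is complete.

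- **Section 8.3, on resumption of IS:** "Participants who have successfully completed IS weaning and who subsequently experience rejection will be re-started on IS". No exception is given for the type of biopsy or for normal liver tests.
- **Section 8.7:** this applies to participants without allograft dysfunction who have a protocol biopsy at 12 or 24 months off IS. Table 5 changes lead back to baseline IS. Participants without Table 5 changes who "fail to meet the primary endpoint on the basis of the histological criteria defined in Table 4 will be maintained off IS" remain so until the end of the study.

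Section 12.1 defines acute rejection histologically, by either of two routes.

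- **Route (a):** "Presence of at least 2 of the following 3 features features according to Banff criteria". The features are portal inflammation, inflammatory bile duct damage, and subendothelial inflammation of portal or central veins. No severity floor or liver-test condition is set.
- **Route (b):** portal and/or lobular inflammation without the other two features. It counts only under conditions, one of which is that "they occur in the presence of allograft dysfunction that rapidly normalizes by the re-initiation of immunosuppressive drug therapy".

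Section 8.6 gives a recommended guideline: "Mild acute rejection should be treated initially with reinstitution of baseline IS". Section 10.10 assigns the Table 5 decision in participants without dysfunction to the central pathologist, and the management reading of for-cause biopsies to local pathologists. Section 4.1.2 explains why mild inflammation at one year may be left untreated under careful biopsy monitoring.

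**The concern.** Both sentences are written as mandatory, and both address participants who have completed weaning. If one biopsy can be rejection under 12.1, a Table 4 failure, and free of Table 5 changes, the protocol gives opposite orders for it. A site that took 8.3 at its word would restart IS; a site that followed 8.7 would not.

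In a withdrawal trial this matters in both directions. Section 4.2 lists untreated rejection among the main risks and describes the harm of chronic IS exposure. Different handling across sites would also make IS exposure depend on the site, in a trial with secondary outcomes such as renal function, co-morbidity, quality of life and cost.

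**Working it through.** The plan gives no figure on this point. The check is whether any biopsy falls under both rules.

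**Step 1. Can rejection be present with normal liver tests?** Route (b) requires dysfunction and route (a) does not. Since the condition is written into only one route, route (a) applies with normal liver tests.

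**Step 2. Which route (a) biopsies fail Table 4?** Two of three features give C(3,2) = 3 pairings.

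| Pairing | Table 4 portal row |
|---|---|
| New portal infiltrate + bile duct damage | Fails: increased portal inflammation with duct damage |
| New portal infiltrate + portal vein endotheliitis | Fails: increased portal inflammation with "appearance of definite venous endotheliitis" |
| Bile duct damage + endotheliitis, no increase in portal inflammation | Not counted: the row is headed by increased portal inflammation |

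So 2 of 3 pairings fail Table 4. This counts combinations of features, not patients.

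**Step 3. Can those two avoid every row of Table 5?** Take mild portal inflammation and go through the rows.

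- *Portal:* the trigger is "Development of moderate portal inflammation or moderate interface activity in most portal tracts". Mild inflammation with less than moderate interface activity does not reach it.
- *Central veins:* perivenulitis in most central veins is required. Endotheliitis confined to portal veins does not count.
- *Bile ducts:* the trigger is "New-onset biliary epithelial cell senescence changes or ductopenia". Inflammatory duct damage without either is not listed.
- *Fibrosis and arteries:* a rise of at least 2 grades, or arteriopathy, is required. Neither need be present.

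Both pairings can therefore show no Table 5 change.

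**Step 4. Apply the two rules to such a biopsy with normal liver tests.**

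| Rule | Condition met? | Instruction |
|---|---|---|
| 8.3 | Yes: rejection after completed weaning | Restart IS |
| 8.7 | Yes: no dysfunction, Table 4 failure, no Table 5 change | Stay off IS to study end |

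**Step 5. Upper bound on exposure.** Follow-up after weaning is 36 months (section 5.5).

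- Finding at 12 months: 36 − 12 = 24 months on versus off IS, at most.
- Finding at 24 months: 36 − 24 = 12 months, at most.

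**Step 6. Effect on the primary endpoint.** A Table 4 failure is a failure of the primary endpoint whether IS is restarted or not, so the endpoint does not change.

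**The case against.** The strongest reply is that the protocol already settles the case. Section 8.7 is the specific rule: it names the population, the biopsies and the outcome. Section 10.10 puts the decision for participants without dysfunction on Table 5 and the central read. Section 4.1.2 gives the clinical reason, and a specific rule prevails over a general bullet in the weaning section. It can also be said that 12.1 defines outcome measures rather than treatment triggers, and that section 6.3 lets the investigator act in the participant's best interest.

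Most of this stands, and it is why the point is small. It does not remove the overlap. Section 8.3 is itself addressed to people who have completed weaning, section 8.6 also diagnoses rejection by Banff biopsy criteria, and neither refers to 8.7. The reason in 4.1.2 concerns changes at 1 year, so for the 24-month biopsy the intent rests on 8.7 and 10.10 alone.

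A reader might infer that 8.6 is a second contradiction, because it bases clinical decisions on local readings and recommends reinstitution for mild rejection. The text does not bear that out. The guideline is only recommended, and its next step depends on whether liver tests improve, which presupposes abnormal tests. Section 10.10 ties local management reads to for-cause biopsies.

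**Conclusion.** The point holds as a minor error of wording. As written, 8.3 and 8.7 give opposite instructions for a protocol biopsy that meets 12.1(a) with only mild portal inflammation, in a participant with normal liver tests. The intended rule can be recovered: 8.7 governs.

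A reader might infer a design fault that leaves safety management undetermined, or a threat to the main result. The documents support neither. The intent is legible from 8.7 with 10.10, and the primary endpoint is the same under both rules. By definition the biopsy shows no Table 5 change, so it does not enter the secondary endpoint on Table 5 re-institution, and its central classification does not depend on which rule a site follows. Rejection that comes with dysfunction, or that meets Table 5, is not affected.

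The number of participants is likely small and cannot be estimated from the protocol. The 24- and 12-month figures are ceilings for a single case. The conclusion assumes that rejection in 8.3 carries its 12.1 meaning, which is the only definition the protocol gives.

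**What to change.** Add to the 8.3 sentence on rejection after completed weaning: *except rejection found only on a protocol biopsy without allograft dysfunction, which is managed under 8.7/Table 5 on the central read*. Put a cross-reference to 8.7 in section 8.6.

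This follows the policy already stated in 8.7, so Tables 4 and 5, the endpoints and the definition of rejection stay as they are. The cost is one clause and one cross-reference, with no extra biopsies, visits or readers. The gain is consistent treatment and IS exposure across sites.
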